### 3.5 Concurrent Therapies

Chemotherapeutic agents, radiation therapy, immunotherapy or investigational anti-cancer agents cannot be administered to patients enrolled on this protocol. If these therapies are administered, the patient will be removed from the study.

### 3.5.1 Surgical Guidelines

Surgery will play an important role in the management of patients enrolled on this protocol. Only patients who have been fully resected, or who are deemed fully resectable, will be eligible to enroll. The surgical oncologist will determine the approach for resection. Oral therapy with saracatinib or placebo will begin following complete resection of all recurrent lung nodules. For patients with bilateral disease who require staged thoracotomies, oral therapy will begin only after the second thoracotomy and only if all nodules have been resected. Patients who recur in the lung while on study and who are thought to be amenable to complete surgical resection will be unblinded. Those patients who were receiving placebo may then have the option of undergoing surgical resection. If fully resected, they will be given the option to begin oral therapy with Saracatinib.

Biological studies to determine the etiology of recurrent osteosarcoma are an important component of this protocol. Prior to any surgery, every attempt should be made to insure that the tumor sample is handled properly, so that all of the studies can be performed (see Sections 3.6.1 and Operations Manual).

## 3.6 Biological Studies

All institutions will send fresh frozen tissue, a corresponding H+E slide, and a blood sample for microarray and sequencing analysis from biopsy and/or time of surgery for patients who have consented, if available (see Sections 3.6.1, 3.6.4, and Operations Manual). Other biological studies will be performed only at the NIH (see Sections 3.6.2 and 3.6.3).

The molecular changes that underlie tumorigenesis have been well studied in many tumor types due to the availability of tumor samples. For pediatric cancers such as leukemia and neuroblastoma, this has resulted in a dramatic improvement in overall survival and marked decrease in treatment related toxicities. The latter is a direct consequence of molecular studies that have resulted in the ability to stratify patients into high-risk, standard-risk and low-risk groups. Overall survival rates in osteosarcoma have also increased remarkably in the last 40 years. However, the identification of biological and genetic surrogates for prognosis, progression and metastasis has been lacking. One of the major reasons for this has been the overwhelming use of neo-adjuvant chemotherapy to treat patients. Initial biopsy samples are so small that the entire sample is usually needed for diagnosis. Samples taken at the time of definitive surgery are large. However, very few samples contain high numbers of viable tumor cells due to the effects of chemotherapy, and many times the sample consists only of a dense non-cellular stroma.

This has greatly hindered the ability to study molecular changes associated with osteosarcoma.

The tumor samples that we expect to analyze will form the largest collection of recurrent osteosarcoma patient samples that have not been subjected to any form of therapy. Many of the studies we have planned can only be performed if the sample is freshly frozen. We therefore request, that treating physicians use the guidelines in this protocol for sample preparation and shipping whenever possible (see Operations Manual).

### 3.6.1 Microarray Analysis

The expression pattern of genes in tumors can provide a wealth of knowledge, especially when they are tied to outcome data. Microarray analysis makes it possible to study the expression of tens of thousands of transcripts. This study will provide the opportunity to increase the biological data for patients with osteosarcoma. Specifically, the large number of untreated samples will make it easier to identify a gene signature to predict for recurrence of osteosarcoma. In addition, the outcome of patients, irrespective of whether they received saracatinib or placebo, will also be known. This allows for the possibility of determining an additional gene signature that predicts for survival. Understanding gene signatures using a large population will help elucidate the pathophysiology of recurrent osteosarcoma and may lead to improvements in the treatment of this disease.

In general, the methodology relies on preparation of RNA, followed by cDNA. Fluorescent labeling followed by hybridization to a DNA chip allows for quantitative scanning for hybridized complexes. The complexity and density of the microarray chips is increasing exponentially, as are the software programs used to analyze these large result files. Therefore, specifics of this experiment will not be addressed, since the technology may improve markedly prior to the point that samples are available for analysis.

For all patients who have consented, samples will be collected, consisting of flash frozen tumor (see Operations Manual, for preparation and shipping instructions) and a corresponding H+E slide. In addition, peripheral blood will also be collected for the preparation of normal DNA from leukocytes. These assays will be performed at the NCI under the guidance of [name]. To maintain the integrity of the blind, at no point, will clinical investigators have access to the results of these studies.

### 3.6.2 Biomarkers Related to Activation of Src and Src Substrates

For patients who are treated at the NIH, immunohistochemistry will be utilized to study the expression of Src and phosphorylated Src in tumor samples. More importantly, the downstream targets of Src will also be examined. These include FAK and paxillin and their phosphorylated forms. Samples will consist of paraffin blocks of tumor tissue. The

assay will be performed under the direction of [name] at the NCI. To maintain the integrity of the blind, at no point, will clinical investigators have access to the results of these studies.

### 3.6.3 Establishment of Cell Lines and Murine Xenografts

For patients who are treated at the NIH, the establishment of cell lines and murine xenografts will be attempted when there is a sufficient amount of tumor sample. Cell lines are a valuable reagent that allow for in vitro and in vivo experiments. These cell lines can be targeted for introduction of exogenous DNA sequences or disruption of endogenous DNA sequences, allowing investigators to verify that distinct genetic changes are causative for tumor progression and metastases. The paucity of human osteosarcoma cell lines testifies to the difficulty in establishing them. In addition, only a handful of osteosarcoma cell lines that grow in cell culture form primary tumors in immunocompromised mice.

The successful generation of a cell line requires immediate processing of the sample. At the NIH, as soon as a surgical sample is removed from the operating room, a pathologist places the sample in media and delivers it to a laboratory technician who has expertise in tissue culture. The sample is minced and added to a tissue culture flask and allowed to propagate. Overgrowing fibroblasts are allowed to grow and detach as they become over-confluent. In several instances, osteosarcoma cells begin to grow rapidly, but this may take up to one year of tissue culture.

Another useful reagent is a primary tumor that forms following surgical implantation of tumor fragments into immunocompromised mice. At the NIH, a protocol has been approved by the animal care committee, allowing for such studies. Tumor samples will be minced and added to a tissue culture flask containing tissue culture media for overnight propagation. The following day, tumor samples will be surgically implanted in the area of the tibia. In several instances, a primary tumor will form at the implantation site. Although it will be impossible to determine the type of treatment that a patient is receiving based these results, at no point will clinical investigators have access to the results of these studies.

### 3.6.4 Sequencing Analysis

Technology is improving so rapidly, that we now have the capability to perform sequencing analysis with the samples that are left over following microarray analysis (see section 3.6.1). In addition to RNA, DNA will also be prepared after comparison to an H+E slide of the corresponding tumor. We will then perform transcriptome sequencing, exon re-sequencing and mate-pair end sequencing, allowing us to detect translocations. The availability of matched normal DNA in the blood will allow us to determine which changes are unique to the tumor. The rapid improvements in genomic sequencing technology makes it impossible to predict what will be the state of the art methodology at the time that the samples are actually tested. Therefore, specifics of this experiment are not addressed.

These tests will be performed for research purposes. All samples will be de-identified prior to submission. Although it is impossible to determine the type of treatment that a patient is receiving based on these results, to maintain the integrity of the blind, at no point will clinical investigators have access to the results of these studies. The results of these tests will not be divulged to the patient or any physician who is involved in clinical care.

### **3.7 Off Study Criteria**

#### **3.7.1 Definition of Disease Progression**

Disease progression is defined as recurrence of osteosarcoma based on radiographic evidence or histologic verification of the recurrent lesion. Disease progression is one of the criteria that results in removal from the protocol.

Patients who recur in the lung while on study and who are thought to be amenable to complete surgical resection will be unblinded.  
(see Section 7.4.2).

Those who were receiving Saracatinib will be taken off study due to disease progression.

Those patients who were receiving placebo, whose recurrence is localized to the lung and who are thought to be completely resectable, will be offered the option of undergoing further surgery followed by therapy with Saracatinib (see Section 3.2.6).

The only curative therapy for patients who have progression of disease, which in this case, is recurrence of tumor, while on saracatinib or placebo, is surgical resection of all recurrent nodules. Therefore, every attempt at complete surgical resection should be attempted in any patient who progresses/recurs. Biological analysis of these tumor samples may prove very informative in determining the etiology of osteosarcoma recurrence. Therefore, at the time of surgery every attempt should be made to send the recurrent tumor sample for biological studies (see Operations Manual). Blood sample for microarray analysis should be collected at time of recurrence only if it was not obtained at baseline. Even though patients who were receiving Saracatinib will be off study due to disease progression, if the patient consents the recurrent tumor sample should still be collected for biological studies if possible.

The date that the patient is randomized will be used as the starting date for measurements of overall survival, progression free survival and time to treatment failure. For cross-over patients, the date that Saracatinib is started will be used as the starting date for measurements of overall survival, progression free survival and time to treatment failure. Progressive disease will be defined as recurrence of osteosarcoma based on radiographic evidence of recurrent nodules. In many cases, initial radiographic scans may not provide clear evidence of recurrence, especially if an infectious etiology is also possible. Once recurrence is verified, either by conclusive radiographic evidence or by histologic

diagnosis, the earliest date of the abnormal radiologic finding will be used as the ending date for measurement of progression free survival and time to treatment failure. Any adverse event that results in discontinuation of either saracatinib or placebo will be considered a treatment failure. This includes toxicity, disease progression or death. The time to treatment failure will begin on the day of randomization, and end on the day of discontinuation of either saracatinib or placebo.

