### Secondary Objectives

- To determine if the addition of saracatinib to pulmonary metastasectomy, versus placebo and pulmonary metastasectomy, results in an increase in overall survival.
- To determine if the addition of saracatinib to pulmonary metastasectomy, versus placebo and pulmonary metastasectomy, results in an increase in the time to treatment failure, defined as a composite endpoint measuring time from randomization to discontinuation of treatment for any reason, including disease progression, treatment toxicity, or death.
- To perform microarray analysis of tumor samples to identify a gene signature that predicts for recurrence of osteosarcoma.
- To evaluate tumor samples for biomarkers related to activation of Src and Src substrates.
- To establish cell lines and murine xenografts from recurrent tumor samples.
- To perform sequencing analysis of DNA and RNA in tumor samples compared to normal blood to detect mutations that may be causative for recurrent osteosarcoma.

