### 3.2.6 Cross-over Regimen for Patients Who Recur in the Lung While On-Study

Patients who recur in the lung while on study, and who are thought to be amenable to complete surgical resection of the recurrent tumor will be unblinded. Those patients who were receiving placebo will then have the option of undergoing surgical resection; if fully resected they will be given the option to begin oral therapy with Saracatinib.

Saracatinib will be administered as a once daily, oral dose of 175 mg, for a 28-day cycle, with no breaks between cycles. The duration of treatment with saracatinib will be thirteen 28-day cycles (364 days total). Cycle 1 Day 1 must commence no later than 6 weeks after the time of the definitive metastasectomy. Patients who cannot commence oral therapy within 6 weeks will be removed from the study.

Biological studies to determine the etiology of recurrent osteosarcoma are an important component of this protocol. Prior to metastasectomy, every attempt should be made to

insure that the tumor sample is handled properly, so that all of the biological studies can be performed (see Sections 3.6.1 and Operations Manual).

Patients who recur in locations other than the lung while on-study will be taken off study and will not be unblinded.

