As explained in section 3.2.6, a subset of patients who recur while receiving placebo will be given the opportunity to receive saracatinib. Since patients on both arms will have received this agent, although at different times in the natural history of their disease, this may result in a lessening of the difference in survival between the arms compared to the case when only patients on one arm received the agent. However, since development of a recurrence may still be associated with overall survival duration, the magnitude of the impact may be limited.

An additional secondary goal is to determine if the addition of saracatinib to pulmonary metastasectomy, versus placebo and pulmonary metastasectomy, results in an increase in the time to treatment failure (TTF). Any adverse event that results in discontinuation of either saracatinib or placebo will be considered a treatment failure. This includes toxicity, disease progression or death.

Again, the randomized nature of the Phase II.5 study will allow us to determine the actual 2-year PFS and 3-year OS rates in patients who receive surgery and placebo, or surgery in combination with saracatinib.

Patients will be stratified based on the following criteria:

Number of Recurrences: FIRST versus SECOND versus THIRD or MORE

Number of Recurrent Nodules: ONE or TWO versus THREE or MORE

The date that the patient is randomized will be used as the starting date for measurements of overall survival, progression free survival and time to treatment failure. Progressive disease will be defined as recurrence of osteosarcoma based on radiographic evidence or histologic verification of the recurrent lesion.

At the first annual opportunity following the point at which 20 patients per arm have been randomized (40 total) and potentially followed for at least 12 months, an interim evaluation for futility will be performed.

The futility evaluation will be performed as follows. Based upon the full data available at that time, a conditional power analysis will be performed to determine if the trial is

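### Section 3.7.1 restarts the OS, PFS and TTF clocks for cross-over (placebo) patients, against the randomisation start date in Section 5.3

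*Combined protocol and SAP*

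**What the plan says.** Section 3.7.1 first makes randomisation the start date for OS, PFS and TTF. Its next sentence gives a different origin for one group: "For cross-over patients, the date that Saracatinib is started will be used as the starting date for measurements of overall survival, progression free survival" and TTF.

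Other places give the randomisation date with no exception for cross-over:

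- Section 5.3, for all three endpoints: "The date that the patient is randomized will be used as the starting date for measurements of overall survival, progression free survival" and TTF.
- The end of Section 3.7.1, for TTF: "The time to treatment failure will begin on the day of randomization, and end on the day of discontinuation of either saracatinib or placebo".
- The Secondary Objectives in the Precis, which define TTF as "time from randomization to discontinuation of treatment for any reason, including disease progression, treatment toxicity, or death".

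On the PFS event, Section 3.7.1 says that once recurrence is verified, "the earliest date of the abnormal radiologic finding will be used as the ending date for measurement of progression free survival" and TTF.

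Cross-over is open only to placebo patients with a resectable lung recurrence (Sections 3.2.6 and 7.4.2). Saracatinib patients who recur go off study. Section 5.3 says that "a subset of patients who recur while receiving placebo will be given the opportunity to receive saracatinib", and warns that "this may result in a lessening of the difference in survival between the arms". It defines no separate analysis of the cross-over cohort.

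**The concern.** The primary endpoint and both time-to-event secondary endpoints have two start-date rules. They differ for one arm only, and the trigger is an outcome after randomisation. A patient who crosses over has two possible PFS times: randomisation to first recurrence, or saracatinib start to a later event. No section says which one enters the log-rank test.

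For OS, the restart alone removes the months that a placebo patient survived before cross-over. That shortens placebo survival and favours saracatinib even if the drug does nothing. For PFS and TTF, moving the start date puts the first recurrence before time zero, so a later event must take its place. The size of the distortion, and for TTF its direction, then depends on when cross-over is allowed. The tests would no longer compare the randomised arms from a common origin. The futility look in Section 5.3, which uses 12-month PFS proportions, has the same ambiguity.

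**Working it through.** **1. The rules side by side**

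| Place | Endpoints | Start date | Cross-over exception |
|---|---|---|---|
| Section 3.7.1, general sentence | OS, PFS, TTF | Randomisation | – |
| Section 3.7.1, next sentence | OS, PFS, TTF | Saracatinib start | Applies to cross-over patients only |
| Section 3.7.1, end | TTF | Randomisation | None |
| Section 5.3 | OS, PFS, TTF | Randomisation | None |
| Precis, Secondary Objectives | TTF | Randomisation | None |

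**2. The plan's own power reproduces with one common origin**

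Inputs from Section 5.3: 44 per arm, 48 months of accrual plus 12 of follow-up, one-sided alpha 0.10.

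- PFS hazards: −ln(0.33)/24 = 0.0462 and −ln(0.53)/24 = 0.0265; ratio 1.746.
- Expected events per arm: 44 × [1 − (e^(−12λ) − e^(−60λ))/(48λ)] = 33.8 and 25.9, total 59.7.
- PFS power: Φ(√59.7 × ln(1.746)/2 − 1.2816) = 80.8%, against 80% stated.
- OS hazards 0.0222 and 0.0099, ratio 2.239, expected events 23.3 and 12.9. Power: Φ(ln(2.239)/√(1/23.3 + 1/12.9) − 1.2816) = about 85%, as stated.

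**3. OS time lost per cross-over patient**

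Assume saracatinib starts 2 months after recurrence. One-year PFS is √0.33 = 0.5745. For recurrences in the first 12 months, the mean time to recurrence plus the lag is

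1/λ − 12 × 0.5745/0.4255 + 2 = 21.65 − 16.20 + 2 ≈ 7.4 months.

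With no time limit, allowing for staggered follow-up of 12 to 60 months, the figure is 14.9 months.

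**4. Simulation of the restart entering the arm tests**

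Model: recurrence, then death; 44 per arm; follow-up uniform on 12 to 60 months.

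- Recurrence hazards are 0.0462 (placebo) and 0.0265 (saracatinib).
- The death hazard q after recurrence solves (q·e^(−36λ) − λ·e^(−36q))/(q − λ) = 3-year OS. This gives q = 0.0572 for 45% (placebo) and 0.0354 for 70% (saracatinib).
- Null runs use the placebo hazards in both arms and a second-recurrence hazard of 0.0462.
- PFS runs use the planned effect and a second-recurrence hazard from 0.0265 to 0.0924. After cross-over, PFS ends at second recurrence or death.
- TTF counts recurrence or death on treatment, is censored at 12 months of each treatment period, and ignores toxicity.
- There are 20,000 trials per null setting and 8,000 per alternative setting.

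The share crossing over (25% / 50%), the lag and the second-recurrence hazard are assumptions; the documents give none. Two windows are shown because Section 5.3 speaks of recurrence while on placebo, whereas Section 3.2.6 covers "Patients who recur in the lung while on study, and who are thought to be amenable to complete surgical resection".

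| Quantity | No restart | 12-month window, 25% / 50% | No limit, 25% / 50% |
|---|---|---|---|
| Mean cross-over patients | – | 4.2 / 8.3 | 7.3 / 14.6 |
| OS type I error, one-sided | 10% | 12% / 14% | 19% / 34% |
| PFS power at HR 1.75 | about 80% | 75–79% / 69–78% | 77–83% / 74–86% |
| TTF type I error, one-sided | 10% | 6% / 4% | 14% / 20% |

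The TTF sign change has a simple cause. Inside 12 months, the restart removes early placebo failures. With no limit, it also gives placebo patients who finished treatment without failure a second period in which to fail.

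A separate 6,000-trial run with the 12-month window gave OS type I error of 12% / 13.5% and PFS power of 76% / 71–74%, in line with the table.

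**The case against.** The strongest reply is that the sentence was never meant for the arm comparison. Cross-over is a second treatment course with its own Cycle 1 Day 1 and its own thirteen cycles, so a start date for that course is natural. The sentence sits under Off Study Criteria. Section 5.3, which specifies the log-rank tests, uses randomisation throughout and expects cross-over to lessen the survival difference, whereas a restarted OS clock would tend to enlarge it. That makes a descriptive second clock a plausible intent. No section states it, however, and read literally the specific rule overrides the general one.

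It is also fair that OS, a secondary endpoint, is the only one distorted by the start date alone. PFS and TTF need a further unwritten step, the replacement of the first recurrence by a later event. For PFS no direction is established across the windows.

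The no-limit scenario is an upper case, since scheduled CT scans end at 36 months. Capping cross-over there gives OS type I error of about 17–19% / 28–30%, which trims the figure but leaves the bias. If the Section 5.3 wording governs, the 12-month window applies and the OS effect is 2 to 4 percentage points. The TTF figures omit toxicity, and the PFS figures count deaths although Sections 3.7.1 and 5.3 define progression only as recurrence. These limits affect the sizes, not the conflict in the text.

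**Conclusion.** The concern holds. Section 3.7.1 gives OS, PFS and TTF a start date for cross-over patients that conflicts with Section 5.3 and, for TTF, with the Precis and with its own closing text. The restart can apply only to the placebo arm, and nothing limits it to a separate analysis.

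The conflict rests on the text alone. The sizes apply only if restarted times enter the arm tests, and they depend on the assumed cross-over share, lag and later hazards. On those terms the clearest harm is to OS, where false-positive risk rises above the nominal 10% in every setting examined. PFS power could move either way when no window applies, and the TTF bias has no fixed sign. The planned power figures are not in dispute; they reproduce with a common randomisation origin.

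**What to change.** Make Sections 3.7.1 and 5.3 say the same three things:

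1. For every randomised patient, OS, PFS and TTF run from randomisation and are analysed by assigned arm.
2. For patients who later cross over, the first recurrence is the PFS event and the end of first-assigned treatment is the TTF event.
3. Any outcome measured from the cross-over saracatinib start date is a descriptive summary of the cross-over cohort and does not enter the comparison of arms or the interim looks.

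The cost is protocol wording only. It needs no new data, does not change the sample size and leaves treatment rules untouched.

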different treatments, including surgery alone, and/or radiation, and/or chemotherapy, and/or high dose chemotherapy with stem cell rescue. Therefore, historical data do not give a true indication of actual survival rates. This study will try to determine whether patients who receive saracatinib will experience a 60% relative increase in progression free survival. Secondary objectives will determine whether patients who receive saracatinib will experience a 56% relative increase in overall survival and an increase in the time to treatment failure. Any adverse event, including toxicity, disease progression and death, that result in discontinuation of either saracatinib or placebo will be considered a treatment failure. The randomized nature of this study will allow us to determine the actual survival rates in these two cohorts, thereby assessing the efficacy of saracatinib in this patient population. Forty-four patients will need to be randomized in each arm, for a total of 88 patients, over a 48-month accrual period. Follow-up for survival of the last patient randomized must continue for an additional year. Patients who recur in the lung while on-study and who are thought to be amenable to complete surgical resection will be unblinded. Those who were receiving placebo will be given the option of undergoing surgical resection. If fully resected, they will be given the option to begin oral therapy with saracatinib.

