#### Criteria for Removal from Protocol:

##### Administrative

- Protocol violations, such as non-compliance with treatment, or required follow-up evaluation, as determined by the Principal Investigator (Contact SARC for non-compliance issues; study PI will review on a case-by-case basis)
- Refusal of further treatment or withdrawal of consent by the patient
- Patient is lost to follow-up

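### Time to treatment failure has stated rules for event, end date and start date that do not agree

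*Combined protocol and SAP*

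**What the plan says.** **Event.** The secondary objectives in the precis define TTF as "time from randomization to discontinuation of treatment for any reason, including disease progression, treatment toxicity, or death". Section 1.2.9 says: "Any adverse event, including toxicity, disease progression and death, that result in discontinuation of either saracatinib or placebo will be considered a treatment failure". Sections 3.7.1 and 5.3 use near-identical words, "Any adverse event that results in discontinuation of either saracatinib or placebo will be considered a treatment failure", and add that toxicity, progression and death are included.

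**End date.** Section 3.7.1 says that once recurrence is verified, "the earliest date of the abnormal radiologic finding will be used as the ending date" for both PFS and TTF. The same paragraph closes with "The time to treatment failure will begin on the day of randomization, and end on the day of discontinuation of either saracatinib or placebo". Section 3.3.2 deals separately with toxicity withdrawals: they are treatment failures, and their total treatment duration goes into TTF.

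**Start date.** Section 5.3 says "The date that the patient is randomized will be used as the starting date for measurements of overall survival", and the sentence goes on to PFS and TTF. Section 3.7.1 says the same and then adds "For cross-over patients, the date that Saracatinib is started will be used as the starting date for measurements of overall survival", again continuing to PFS and TTF.

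No section says which wording takes precedence.

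**The concern.** Two analysts working from different sections would draw different event counts and failure dates from the same patients. Nothing in the plan prevents the choice being made after the data are seen.

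The event rule decides whether stops unrelated to an adverse event count as failures. The end-date rule decides when a recurrence on treatment is timed. The start-date rule matters most if applied literally in the randomised comparison. It would then replace a failure that occurred on placebo with a later clock, in one arm only, and the same sentence covers PFS and overall survival.

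**Working it through.** The plan states no TTF sample size, event count or power, so there is no TTF figure to reproduce. The sizes below use the PFS design hazards, so those were checked first.

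**Design inputs (Section 5.3).** Two-year PFS is 33% v 53%, with 44 patients per arm, 48 months of accrual, 12 further months of follow-up and a one-sided 0.10 log-rank test.
- Hazards: −ln(0.33)/24 = 0.0462 and −ln(0.53)/24 = 0.0265 per month; ratio 1.75. These match the plan.
- Event probability with uniform accrual: 1 − [exp(−12λ) − exp(−60λ)]/(48λ). Expected events: 33.8 + 25.9 = 59.7.
- Schoenfeld power: Φ(√59.7 × ln(1.746)/2 − 1.282) = Φ(0.87) = 0.81, against the stated 80%. The PFS figures reproduce.

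**1. Event rule.** The reasons for stopping, set against the two wordings:

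| Reason for stopping | Where | Precis | 1.2.9, 3.7.1, 5.3 |
|---|---|---|---|
| Progression, toxicity, death | 3.7.2 | failure | failure |
| "Refusal of further treatment or withdrawal of consent by the patient"; non-compliance | 3.7.2 | failure | not clear, unless an adverse event lies behind it |
| Physician decision | 3.7.2 | failure | not clear |
| Prohibited anti-cancer therapy | 3.5 | failure | not clear |
| Pregnancy | 3.7.2, 4.3 | failure | usually not; 4.3 does not treat it as an adverse event, with one exception |

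The documents give no stopping rates, so these are assumed: a net risk c of 5%, 10% or 15% by day 364 for stops in the not-clear rows, and x of 0%, 10% or 20% for toxicity, equal in both arms and independent. With T = 364/30.4375 = 11.96 months, g = −ln(1−c)/T, k = −ln(1−x)/T and h = λ + g + k:
- events that depend on the wording, per arm: 44 × (1 − e^(−hT)) × g/h
- events that count either way, per arm: 44 × (1 − e^(−hT)) × (λ + k)/h

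Example, c = 10% and x = 0, so g = 0.0088:
- Placebo: h = 0.0550, 44 × 0.482 = 21.2 stops, of which 3.4 depend on the wording.
- Saracatinib: h = 0.0353, 44 × 0.344 = 15.1 stops, of which 3.8 depend on the wording.
- Total: 7.2, beside 17.8 + 11.4 = 29.2 progressions.

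Events that depend on the wording / events that count either way:

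| Toxicity stops | c = 5% | c = 10% | c = 15% |
|---|---|---|---|
| 0% | 3.6 / 29.9 | 7.2 / 29.2 | 10.8 / 28.4 |
| 10% | 3.4 / 35.5 | 6.8 / 34.7 | 10.3 / 33.8 |
| 20% | 3.2 / 41.1 | 6.5 / 40.2 | 9.8 / 39.2 |

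Stops at equal rates in both arms also dilute the contrast if counted. With no toxicity stops, the ratio (0.0462 + g)/(0.0265 + g) is 1.64, 1.56 or 1.49 for c = 5%, 10% or 15%, instead of 1.75.

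**2. End date.** Expected progressions within 364 days are 44 × (1 − e^(−0.0462×11.96)) = 44 × 0.424 = 18.7 on placebo and 44 × 0.271 = 11.9 on saracatinib, 30.6 in all. For each, the two dates differ by the time from first abnormal scan to drug stop. Section 3.7.1 itself says that early scans may be inconclusive, so the gap need not be zero. The documents give nothing from which to size it.

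**3. Start date.** By the time a cross-over patient starts saracatinib, recurrence on placebo has already ended that patient's first TTF. The later date can therefore only open a second measurement. Used as the patient's single TTF, it would delete the placebo failure. The share of recurrent placebo patients who cross over is not given. If it is 25%, 50% or 75% (assumed) of the 18.7, then 4.7, 9.3 or 14.0 patients have two stated start dates.

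**The case against.** **Event.** The adverse-event wording says that such events count and lists what they include; it does not say that nothing else counts. That is right. A reader might infer that Sections 1.2.9, 3.7.1 and 5.3 admit adverse events only, but that word is not there. The supportable statement is that other stops are failures in the precis and not clearly failures elsewhere.

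**End date.** The two sentences can be read as a specific rule for recurrence followed by a general rule, and Section 3.3.2 already covers toxicity. This is a sensible reading, but the text does not state it. The sentence before the closing rule lists progression among the failures to which that rule would apply.

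**Start date.** Section 5.3 says that cross-over may lessen the survival difference between arms. That makes sense only if patients stay in their randomised arm on the original clock. Section 3.7.1 also repeats randomisation as the TTF start after the cross-over sentence. A separate cross-over measurement is therefore the likelier intent. A reader might infer that the plan will restart the clock in the primary PFS comparison; the documents do not support that as the intention. What stands is that no sentence limits the second clock.

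**Completers.** A reader might infer that patients who finish 13 cycles could be followed for later recurrence under TTF, with a large effect on event count and power. The documents do not support this: every definition of a failure ties it to stopping drug, and a recurrence after planned completion cannot cause that. Completion needs only a clarifying clause.

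**Weight.** TTF is an unpowered secondary endpoint in a trial that Section 1.2.9 describes as not definitive. This limits the importance of the point but does not remove the conflict.

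**Conclusion.** The concern holds in a limited form. The precis and the other three sections differ on which stops count. Section 3.7.1 gives two end dates without separating their scope. It also gives a cross-over start date, for all three time-to-event endpoints, that Section 5.3 does not.

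About 3 to 11 events turn on the event wording, under the assumed stopping rates. About 31 patients at the design hazards could have two end dates, by an unknown margin. The start-date conflict does harm only if applied literally in the randomised comparison; it would then distort PFS and overall survival as well as TTF.

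The stated sample size of 88 and the PFS power are unaffected, since they rest on a clock from randomisation and do not use TTF. The textual conflicts are certain; the event counts for the first item rest on assumed rates. This should be corrected, but it does not put the design in doubt.

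**What to change.** - **One definition** in the precis and Sections 1.2.9, 3.7.1 and 5.3: time from randomisation to the earliest of recurrence (dated as for PFS), permanent discontinuation of assigned drug before completing planned treatment for any reason, or death. Counting any reason avoids judging why a patient stopped. If the adverse-event wording is preferred, change the precis to match and say how other stops are handled.
- **End date:** limit the day-of-discontinuation sentence in Section 3.7.1 to failures other than recurrence. Align Section 3.3.2 so that toxicity failures are also timed from randomisation.
- **Start date:** state that all randomised comparisons of overall survival, PFS and TTF start at randomisation, and that the cross-over start date serves only a separate descriptive analysis.
- **Completion:** state that finishing 13 cycles is not a failure and that such patients are censored at that point.

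The cost is protocol wording only. Randomisation, scan, drug-stop and death dates are already needed for the trial, so no new assessment is required.
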